8.2.2. Exclusion Criteria

There are no exclusion criteria for this study.

8.3. Variables

The following variables will be collected in an eCRF.

8.3.1. Physician Characteristics

The following variables will be collected once for each physician participating in the study:

- Geographic region (ie, Northeast, Midwest, South, West, Other).
- Practice setting (ie, academic-based, community-based).
- Practice size (ie, solo [1 physician], small [2-10 physicians], medium [11-50 physicians], large [≥ 51 physicians]).
- Years in practice since completion of oncology training (ie, <1 year, 1-5 years, 6-10 years, 11-20 years, >20 years).
- Total number of unique advanced RCC patients seen per year.
- Percentage of advanced RCC patients prescribed first-line axitinib in combination with IO therapies in the past year.

8.3.2. Baseline Patient Characteristics

The following variables, to the extent they are available, will be assessed during the baseline period or on the index date:

Demographics

- Month and year of birth (to calculate age at time points of interest).
- Sex (ie, male, female).
- Weight.
- Height.
- Race/ethnicity (ie, American Indian or Alaska Native, Asian, Black or African American, Hispanic or Latino, Native Hawaiian or other Pacific Islander, White, Other).
- Insurance type (ie, employer, private/non-group, Medicaid, Medicare, military, uninsured, other).

Clinical characteristics

- Date of advanced RCC diagnosis.
- Date of first-line axitinib/IO combination therapy initiation.
- IO agent used in combination with axitinib treatment.
- Initial dose of axitinib.
- Histological type (ie, non-clear cell, clear cell).
- Sarcomatoid differentiation.
- Nephrectomy status.
- Number of metastatic sites and site locations.
- TNM stage according to American Joint Committee on Cancer (AJCC) staging system.
 - Nodal status.
- Fuhrman grade.
- Largest tumor size.
- Necrosis status of the primary tumor (ie, macroscopic, microscopic).
- Microvascular invasion.

- Comorbidities used to derive the NCI Comorbidity Index:
 - Acquired immunodeficiency syndrome (AIDS);
 - Acute myocardial infarction;
 - Cerebrovascular disease (CVD);
 - Chronic obstructive pulmonary disease (COPD);
 - Congestive heart failure (CHF);
 - Dementia;
 - Diabetes;
 - Diabetes with complications;
 - History of myocardial infarction;
 - Mild liver disease;
 - Moderate/severe liver disease;
 - Paralysis (hemiplegia or paraplegia);
 - Peptic ulcer disease;
 - Peripheral vascular disease;
 - Renal disease;
 - Rheumatologic disease.
- Eastern Cooperative Oncology Group (ECOG) performance status.
- Variables to calculate prognostic risk score (ie, Memorial Sloan Kettering Cancer Center [MSKCC] risk or International Metastatic Renal Cell Carcinoma Database Consortium [IMDC] risk).
 - Time from RCC diagnosis to initiation of first-line treatment;
 - Karnofsky performance status;
 - Serum hemoglobin level;
 - Correct calcium level;

- Neutrophil count;
- Platelet count.

8.3.3. Characterization of AEs

The following variables, to the extent they are available, will be assessed during the observation period:

- Type of AE, as defined by Common Terminology Criteria for Adverse Events (CTCAE):
 - Diarrhea, characterized by an increase in frequency and/or loose or watery bowel movements;
 - Fatigue, characterized by a state of generalized weakness with a pronounced inability to summon sufficient energy to accomplish daily activities;
 - Nausea, characterized by a queasy sensation and/or the urge to vomit;
 - Hypertension (new and worsening), characterized by a pathological increase in blood pressure;
 - Palmar-plantar erythrodysesthesia (hand-foot syndrome), characterized by redness, marked discomfort, swelling, and tingling in the palms of the hands or the soles of the feet.
- Serious AE.
 - As specified by the FDA, an AE is considered serious when the patient outcome is: death, life-threatening, hospitalization (either initial admission or prolongation of hospitalization), disability or permanent damage, or congenital anomaly/birth defect.
 - Date(s) of AE onset.
 - Date(s) of AE resolution.

8.3.4. Management Strategies for AEs

The following variables, to the extent they are available, will be assessed during the observation period:

- Type of management strategy:
 - No action for axitinib and IO therapy;

- No action for axitinib, but treatment modification for IO therapy (ie, treatment interruption, treatment discontinuation);
- Axitinib dose reduction, but no action for IO therapy;
- Axitinib treatment interruption, but no action for IO therapy;
- Axitinib treatment discontinuation, but no action for IO therapy;
- Axitinib dose reduction, and treatment modification for IO therapy;
- Axitinib treatment interruption, and treatment modification for IO therapy;
- Axitinib treatment discontinuation, and treatment modification for IO therapy.
- Treatment modification for axitinib:
 - Date(s) of dose reduction;
 - Modified dosage of axitinib;
 - Date(s) when treatment was halted and reinitiated;
 - Date(s) treatment was discontinued.
- Treatment modification for IO therapy:
 - Date(s) when treatment was halted and reinitiated;
 - Date(s) treatment was discontinued.

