7. RESEARCH QUESTION AND OBJECTIVES

The specific objectives of the study are as follows:

1. Describe incident AEs experienced among patients with advanced RCC who received first-line axitinib in combination with IO therapies.
 - Type and seriousness of AEs (ie, diarrhea, fatigue, hypertension, nausea, palmar-plantar erythrodysesthesia [hand-foot syndrome]).

- Proportion of patients who experienced repeated AEs.
- Time from treatment initiation to AE onset, overall and by type and seriousness of AEs.

2. Among patients with advanced RCC who developed incident AEs while receiving first-line axitinib in combination with IO therapies, characterize and describe management strategies for AEs, stratified by type and seriousness of AEs.

- Proportion of patients who used each of the following management strategies:
 - No action for axitinib and IO therapy;
 - No action for axitinib, but treatment modification for IO therapy (ie, treatment interruption, treatment discontinuation);
 - Axitinib dose reduction, but no action for IO therapy;
 - Axitinib treatment interruption, but no action for IO therapy;
 - Axitinib treatment discontinuation, but no action for IO therapy;
 - Axitinib dose reduction, and treatment modification for IO therapy;
 - Axitinib treatment interruption, and treatment modification for IO therapy;
 - Axitinib treatment discontinuation, and treatment modification for IO therapy.
- Average axitinib dose reduction (absolute and percentage change), where applicable.
- Duration of treatment interruption, where applicable.

3. Assess the frequency of and time to AE resolution (from AE onset and initiation of management strategy, separately) among patients with advanced RCC who developed incident AEs while receiving first-line axitinib in combination with IO therapies according to different management strategies implemented, stratified further by type and seriousness of AEs, as allowed by sample size.

[figure not shown]
The above objectives will also be conducted for repeated AEs of the same type.

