8.7.4. Analysis of Resolution of AEs

The proportion of patients achieving resolution of AEs will be described, overall and by type and seriousness of the AEs. The time to resolution from AE onset and from initiation of management strategy will be calculated for all AEs experienced including repeated AEs. The time to resolution of AE (from the onset of AE and from the initiation of management strategies) will be separately estimated using Kaplan-Meier analysis; median time to event will be reported. Analyses will be conducted separately by type of management strategy.

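### Axitinib interruption and discontinuation are not defined by what is known at the halt, so resolution reported by these groups may condition on later restart

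*Combined protocol and SAP*

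**What the plan says.** Section 8.3.4 (also Objective 2 in Section 7) gives axitinib interruption and axitinib discontinuation their own categories, each crossed with whether the IO agent was modified. Two of the categories are "Axitinib treatment interruption, but no action for IO therapy" and "Axitinib treatment discontinuation, but no action for IO therapy". The dates collected for axitinib include "Date(s) when treatment was halted and reinitiated" and, separately, "Date(s) treatment was discontinued".

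Objective 3 asks for frequency of and time to resolution "according to different management strategies implemented, stratified further by type and seriousness of AEs, as allowed by sample size". Section 8.7.4 carries this out: "The time to resolution of AE (from the onset of AE and from the initiation of management strategies) will be separately estimated using Kaplan-Meier analysis", with separate analyses for each type of strategy. The outcome is the field "Date(s) of AE resolution" in Section 8.3.3.

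The documents do not say:
- what distinguishes an interruption from a discontinuation on the day axitinib is stopped;
- whether the label is the decision made at that time or is read off the later course;
- how to class a halt still open when observation ends. Under Section 8.1 it ends at second-line therapy, death, loss to follow-up or abstraction.

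**The concern.** A Kaplan-Meier curve that starts at the halt needs groups that are known at the halt. The recorded dates that separate these two groups, a restart or a discontinuation, may fall later. The oncologist completes the form in retrospect (Sections 8.1 and 8.4) and may already know whether the drug was restarted and whether the AE resolved.

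If the label follows the later course, and restart tends to follow resolution, halts whose AE resolves early collect under interruption and halts whose AE persists collect under discontinuation. The two curves then separate even when the resolution process is the same in every patient. Starting the clock at the strategy does not help, because the label is settled only after that start.

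This matters because the rationale (Section 6) names dose reductions and treatment interruptions as the means of managing AEs that the study sets out to describe, and the artefact favours interruption. The limitations in Section 8.9 do not mention it.

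**Working it through.** The plan gives no resolution times, restart rates or share of permanent stops, so it has no figure to reproduce. Every input below is an assumption, chosen to show direction and range. In both checks all halts share one resolution process, so the true difference between labels is nil.

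**Check 1: closed form, strong dependence.** Time from halt to resolution is exponential with median m days, so S(t) = 2^(−t/m) and F(t) = 1 − S(t). A share p of halts is permanent from the start and labelled discontinuation. Each other halt is labelled interruption if resolved by day 60, and discontinuation if not.

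- Resolved by day 30, interruption: F(30)/F(60).
- Resolved by day 30, discontinuation: p·F(30) / [p + (1−p)·S(60)].

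For m = 28: F(30) = 0.524, F(60) = 0.774, S(60) = 0.226.
- Interruption: 0.524/0.774 = 68%.
- Discontinuation, p = 0.10: 0.0524/(0.10 + 0.90 × 0.226) = 0.0524/0.304 = 17%.
- Discontinuation, p = 0.50: 0.262/(0.50 + 0.50 × 0.226) = 0.262/0.613 = 43%.

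For m = 14: F(30) = 0.774, F(60) = 0.949, S(60) = 0.051.
- Interruption: 0.774/0.949 = 82%.
- Discontinuation, p = 0.10: 0.0774/(0.10 + 0.90 × 0.051) = 0.0774/0.146 = 53%.
- Discontinuation, p = 0.50: 0.387/(0.50 + 0.50 × 0.051) = 0.387/0.526 = 74%.

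The medians come from setting the survival function within each label to one half.

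| True median (days) | Permanent from start | Resolved by day 30, interruption v discontinuation | Median in days, interruption v discontinuation |
|---|---|---|---|
| 28 | 10% | 68% v 17% | 20 v 76 |
| 28 | 50% | 68% v 43% | 20 v 38 |
| 14 | 10% | 82% v 53% | 13 v 26.5 |
| 14 | 50% | 82% v 74% | 13 v 15 |

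**Check 2: simulation, dependence varied.** There were 200,000 halts per scenario, with time in months. True median resolution was 0.5, 1 or 2; median time to a permanent-stop decision 1 or 3; restart 0.25 after its trigger; follow-up after the halt uniform over 1 to 18. A halt was labelled interruption if restart came before both the permanent-stop decision and the end of follow-up, otherwise discontinuation. The share of restarts triggered by resolution was 0%, 50% or 100%. The ranges below span the two permanent-stop settings.

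| True median | 0% triggered | 50% triggered, interruption v discontinuation | 100% triggered, interruption v discontinuation |
|---|---|---|---|
| 0.5 | medians agree | 0.40–0.46 v 0.65–0.72 | 0.33–0.42 v 0.82–0.97 |
| 1.0 | medians agree | 0.68–0.85 v 1.29–1.45 | 0.49–0.71 v 1.58–1.97 |
| 2.0 | medians agree | 1.08–1.45 v 2.44–2.84 | 0.64–1.09 v 2.84–3.73 |

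Across the 50% and 100% scenarios the ratio of medians runs from 0.72/0.46 = 1.6 to 2.84/0.64 = 4.4. At 0% the medians agree to within 0.01. The crude proportion resolved can still differ slightly (at most 90% v 85%, for a true median of 2 and a permanent-stop median of 3), because a halt must be followed long enough to show a restart.

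With all halts in one group from the halt date, the Kaplan-Meier median returned the true value to within 0.01 in every scenario.

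**The case against.** The strongest reply is that the plan does not state the labelling rule on which the bias depends. Type of management strategy is a variable in its own right in Section 8.3.4, discontinuation has its own date field, and the halt and restart dates are needed anyway for the duration of interruption. The label could be the physician's decision at the time. This stands: labelling by later restart is an inference. Equally, nothing in the plan requires a label fixed at the halt.

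Second, no section says that restart depends on resolution. This also stands, and the size of the artefact rests on it. Check 1 is a strong case, since resolution fixes the label of 90% of halts when p = 0.10. With p = 0.50 the day-30 gap for the 28-day median falls from 51 to 25 percentage points.

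Third, Section 8.7.3 foresees multiple strategies per patient. An interruption that later became a discontinuation might be recorded under both, which would keep unsuccessful interruptions in the interruption group. The plan does not say how such an AE enters the curves, so this is possible protection only.

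Fourth, Section 8.5 calls all analyses descriptive, with no hypotheses tested. That rules out a false-positive test but not a misleading pair of medians. The pilot in Section 8.4.1 allows changes to the form and the analysis, but does not name this issue.

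Two stronger readings are tempting. A reader might infer that the plan sorts patients by the outcome itself. It does not: an AE can resolve after discontinuation, and axitinib can be restarted before resolution. A reader might also extend the point to IO halts. Objective 2 and Section 8.3.4 place IO interruption and discontinuation in one treatment-modification level, so no such contrast is planned.

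**Conclusion.** The concern holds as a conditional one. The plan reports resolution separately for two groups whose labels are not fixed at time zero, and no section prevents the label from following later restart. If it does, and restart tends to follow resolution, interruption looks better than discontinuation with no true difference. Under the assumptions tried, the day-30 gap ranges from 8 percentage points (82% v 74%) to 51 (68% v 17%), and the ratio of medians in the simulation from 1.6 to 4.4. With no dependence the medians show no artefact. The documents therefore support saying that the contrast may be biased towards interruption; they do not support saying that it will be, or by how much.

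It should be settled in the analysis plan before the results are produced.

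**What to change.** For Objective 3 and Section 8.7.4:

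- Make the main resolution analysis one 'axitinib halted' group (interruption and discontinuation combined), with and without IO modification. Time it from AE onset and from the halt date, and include halts still open at the end of observation.
- Report restart as an outcome of the halt: whether it occurred, and time to restart.
- Keep the interruption/discontinuation split for the Objective 2 counts.
- If resolution is also shown by the split, label it as descriptive and subject to this bias. An item on the case report form asking what the chart documented at the halt about temporary or permanent intent could support that display. It is only a partial remedy: hindsight may affect it, and Section 8.9 says entries cannot be audited.

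The cost is analysis-plan wording and, optionally, one form item. No additional patients are needed and no clinical rule changes. The downside is that the main analysis no longer reports resolution separately for interruption.

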8.4. Data Sources

AG will contract with a physician panel vendor, Medefield America Limited LLC, to conduct an oncologist panel-based medical chart review in the US. Medefield has access to a large panel of physicians in a wide range of geographic locations. Oncologists will be recruited based on their medical specialty and selected for the study based on the eligible criteria. Each oncologist will complete eCRFs for up to three patients, with each chart review taking approximately 30 minutes to complete. The study will be double-blinded (physicians will be blinded to study sponsor and study sponsor will be blinded on physicians recruited to participate).

Oncologists will abstract data from medical charts of eligible patients using an online eCRF, which AG and the physician panel vendor will jointly develop specifically for this study. Medefield will set up a web-based portal with consistency checks, quality control, and validation processes built into the eCRF to ensure data quality. To capture all relevant information necessary for the study objectives, the eCRF may include both structured

(eg, multiple choice, select all options that apply) and unstructured fields (eg, open-ended responses).

8.4.1. Pilot Test

Prior to launch of data collection, a pilot test will be conducted with up to three oncologists, who will be abstracting data from patient charts. The purpose of the pilot test is to ensure that the questions in the eCRF are clear and interpreted correctly by the oncologists. Oncologists participating in the pilot test will have the ability to comment on the questions they do not fully understand and to provide suggestions on improving the questions. The pilot test will also help ensure that key data elements are contained in patient charts, such that key data elements of this study could be obtained in a reliable manner through the patient chart abstraction.

Upon completion of the pilot test, AG will clean and analyze the data in order to evaluate their adequacy and quality for addressing the study objectives. Further discussions with Pfizer will take place to discuss these findings and potential updates to the eCRF. Changes to the eligibility criteria as well as alternative analytical approaches that are more suitable for the available data may also be considered. Based on this assessment, the study protocol and the eCRF may be updated as needed.

8.5. Study Size

Approximately 200 oncologists may be recruited by the physician panel vendor to abstract medical charts. AG anticipates to obtain data from the medical charts of 400-600 patients with advanced RCC. No formal sample size computation was performed as all statistical analyses are descriptive in nature and no hypotheses are being tested.

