Yet, recent advancements in immuno-oncology (IO) therapeutic agents have changed the treatment paradigm for advanced RCC. IO therapies work by blocking immune checkpoints (eg, programmed death-1 [PD-1]/PD-ligand 1 [PD-L1]) and restoring tumor-specific T-cell-mediated immune responses,^{16,17} and have demonstrated antitumor activity and durable responses in patients with advanced RCC.^{18,19} Specifically, the KEYNOTE-426 trial demonstrated that treatment-naïve advanced RCC patients who were treated with axitinib in combination with pembrolizumab had significantly longer overall survival, progression-free survival, and objective response rate compared to sunitinib,²⁰ leading to US Food and Drug Administration (FDA) approval of axitinib in combination with pembrolizumab for first-line advanced RCC treatment in April 2019. In addition, the JAVELIN Renal 101 trial showed significantly longer progression-free survival among advanced RCC patients who received avelumab plus axitinib than with sunitinib in first-line,²¹ leading to FDA approval of axitinib in combination with avelumab for first-line advanced RCC treatment in May 2019.

While axitinib has generally demonstrated a favorable tolerability profile in real-world studies,^{22,23} there is currently limited information on the real-world adverse event (AE) profile of axitinib in combination with IO therapies. In addition, the effect of dose reductions and treatment interruptions used to manage and resolve AEs occurring among patients with advanced RCC who use axitinib in combination with IOs is not well understood. Given this gap in the literature, AG will conduct a physician panel-based chart review to describe how dose reductions or treatment interruptions related to axitinib (in combination with IO therapy including avelumab or pembrolizumab) can be implemented to potentially manage and resolve AEs occurring among patients with advanced RCC. In this way, the study could help demonstrate that AEs associated with axitinib may be mitigated without excess use of healthcare resource use or additional treatment burden to patients beyond modifications related to axitinib.

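### Proportions and Kaplan-Meier medians are planned with no measure of precision, so chance differences between management-strategy groups can be read as real

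*Combined protocol and SAP*

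**What the plan says.** Section 8.5 states: "Approximately 200 oncologists may be recruited by the physician panel vendor to abstract medical charts", and "AG anticipates to obtain data from the medical charts of 400-600 patients with advanced RCC". It then explains why no sample size was computed: "all statistical analyses are descriptive in nature and no hypotheses are being tested".

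The planned summaries are in Section 8.7:

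- 8.7.1: mean (SD), median (IQR) and frequency distributions for physician and patient characteristics.
- 8.7.2: frequencies and proportions of AEs by IO agent, and mean (SD) and median (IQR) time to onset.
- 8.7.3: frequencies and proportions of management strategies, overall and by AE type and seriousness.
- 8.7.4: the proportion of patients whose AEs resolve, and a Kaplan-Meier analysis of time to resolution from which "median time to event will be reported". Analyses are run separately for each strategy, and repeated AEs are included.

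Objective 3 in Section 7 asks how often and how fast AEs resolve under each strategy, "stratified further by type and seriousness of AEs, as allowed by sample size". Sections 7 and 8.3.4 list eight strategies, and Section 8.2.1 lists five AE types. On the sampling side, Section 8.4 says: "Each oncologist will complete eCRFs for up to three patients".

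**The concern.** None of these sections plans a confidence interval or standard error for any proportion or median. SD and IQR show how patients differ from one another, not how well a group's value is estimated. Nothing allows for several charts from one oncologist, or for several AEs from one patient. Section 8.9 discusses measurement error, missing data, self-reporting and selection, but not sampling error. Section 8.8 mentions an analysis plan, but Annex 1 lists no stand-alone document that could supply the intervals.

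The descriptive aim answers a different question. It explains why no power was computed. It does not remove the sampling error of an estimated proportion or median. The report will set resolution results for up to eight strategies next to each other, and Section 6 hopes that "the study could help demonstrate that AEs associated with axitinib may be mitigated". A reader given eight bare percentages or medians has no means of judging which differences are larger than chance would produce.

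**Working it through.** **The plan's own figure.** 200 oncologists × 2 charts = 400, and 200 × 3 = 600. The range of 400-600 reproduces. The maximum of three is stated and the mean of two is implied. The plan gives no precision figure to reproduce.

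**Group sizes** (assumed: even spread, one AE per patient).
- By strategy: 400/8 = 50 to 600/8 = 75.
- By strategy and AE type: 50/5 = 10 to 75/5 = 15.
- By seriousness as well: 10/2 = 5 to 15/2 = 7.5.

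**Half-width of a 95% interval for a proportion near 50%:** 1.96 × √(0.25/n).

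| n | Half-width (points) |
|---|---|
| 600 | 4.0 |
| 400 | 4.9 |
| 75 | 11.3 |
| 50 | 13.9 |
| 15 | 25.3 |
| 10 | 31.0 |

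**Chance gap among eight equal groups.** Let X be binomial(n, p) with distribution function F, the same for all eight groups and independent between them. Then P(max − min ≤ d) = Σₐ {[F(a+d) − F(a−1)]⁸ − [F(a+d) − F(a)]⁸}, summed over a = 0 to n. With d one event short of 20 points (d = 14 at n = 75, d = 9 at n = 50), the probability of a gap of at least 20 points is one minus this sum. The documents give no resolution rate, so p is assumed, with a range:

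| True resolution in all groups | n = 75 | n = 50 |
|---|---|---|
| 50% | 26% | 55% |
| 70% | 16% | 43% |
| 80% | 6% | 25% |
| 90% | 0.2% | 3% |

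At p = 70% the figure is 97% for n = 15 and 99% for n = 10.

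**Kaplan-Meier medians of two groups with the same true distribution.** Assumed: true median 28 days, uniform censoring between 30 and 300 days, and a Weibull shape from 1 (exponential) to 2. None of these comes from the documents. The result is the share of simulations in which the larger observed median is at least 1.5 times the smaller:

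| Shape | n = 12 | n = 50 |
|---|---|---|
| 1 | 50% | 17% |
| 1.5 | 31% | 4% |
| 2 | 18% | 1% |

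Separate runs of the simulation gave 49-51% and 18-19% at the two ends for n = 12.

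**Clustering by oncologist.** The design effect is 1 + (m − 1) × ICC. The documents give no ICC, so 0.1-0.3 is assumed. It runs from 1 + 1 × 0.1 = 1.1 to 1 + 2 × 0.3 = 1.6, which multiplies interval widths by √1.1 = 1.05 to √1.6 = 1.26, a widening of 5-26%. Inside a strategy-by-type cell few charts share an oncologist. In a simulation of 200 oncologists with three charts each, with ICC 0.3 for strategy and outcome and AE type independent (all assumed), the effective cluster size was about 1.15, giving 1 + 0.15 × 0.3 ≈ 1.05.

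**The case against.** The study is descriptive, plans no contrast between strategies and tests nothing. Section 6 says it will describe how axitinib modifications are used, and its hope of demonstrating something concerns mitigation without added resource use or treatment burden. A reader might infer that the study sets out to rank strategies. No section says so, and the point should not rest on that.

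A reader might also infer that up to 8 × 5 × 2 = 80 tiny cells are certain to be reported. They are not: the split of resolution by strategy and by AE type and seriousness is made conditional on sample size. With multiple and repeated AEs per patient, cells will also hold more events than the patient averages above. What remains is that the condition names no minimum, so the choice of cells can be made after the results are seen, and that the analysis by strategy in 8.7.4 carries no such condition.

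The simulated medians depend heavily on shape. At n = 50 the chance of a 1.5-fold difference between one given pair falls from 17% for the exponential to about 1% at shape 2. That stands, and it is why a range is shown. It covers one pair only; the gap between the extremes of eight groups is wider.

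Clustering might be taken as a fault of equal weight. The figures do not support that, since it adds 5-26% to interval width overall and less in small cells. Nor do the documents show that each abstracting oncologist chose the strategy; Section 8.2.1 asks only for an oncology specialty and access to complete records.

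Lastly, the missing sample size computation in 8.5 is not itself a fault in descriptive work.

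**Conclusion.** The point holds as a matter of precision. Every proportion and every Kaplan-Meier median in 8.7.2 to 8.7.4 is planned without an interval. At the size of the strategy groups the sampling error is not negligible: about 11-14 points either way for a proportion near 50%, and a 16-43% chance of a spurious best-to-worst gap of at least 20 points at 70% true resolution. The gap figure is lower if resolution is very common and higher if it is near 50%. Both figures assume an even split, one AE per patient and independent charts. Real groups will be unequal, so some will be larger and others smaller than 50-75. If the split by AE type is shown, half-widths reach about 25-31 points, and two strategies with the same true median differ at least 1.5-fold in roughly one fifth to one half of simulations at n = 12, depending on the assumed shape.

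The documents support saying that chance differences can be read as real, not that they will be. The estimates themselves remain valid to compute. The change should be made, but the study does not fail without it.

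**What to change.** - In 8.7.2 to 8.7.4, report a 95% confidence interval with each AE, management-strategy and resolution proportion and with each Kaplan-Meier median.
- Obtain the intervals from a bootstrap that resamples oncologists. Keeping all of an oncologist's charts together also covers multiple and repeated AEs within a patient. Where a cell shows 0% or 100%, the bootstrap interval has zero width, so name a second method (for example Wilson) for those cells.
- Add an anonymous physician code to the data export. Section 8.3.1 already collects physician variables once per physician, and nothing in 8.6 rules out an arbitrary code, though no section says that one is exported.
- Give Objective 3's sample-size condition a minimum cell size, chosen by the sponsor before data are seen, below which only counts are shown.
- In 8.5, add the expected half-widths for 400-600 charts and for the strategy groups.

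No further charts are needed, and Section 8.4.1 already provides for protocol updates after the pilot. The cost is a little programming and wording. The downside is that small-group results look less certain and some medians are not shown.
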